9.3 Recording and reporting of SAEs, SARs AND SUSARs

All SAEs/SARs/SUSARs occurring from the time of perfusion of the treatment into the aortic root until 24 hours post-transplant must be recorded on the electronic AE Form **within 24 hours** of the research staff becoming aware of the event. NB 24 hours post has been chosen because all the IMP is washed out on reperfusion of the heart and cannot reasonably be expected to still be present or have any direct effect beyond 24 hours. "Post-transplant" will be defined as the time the recipient leaves the operating theatre after they receive their transplant or death where this

occurs during the transplant implantation. Death during the implantation would be considered a SAE and should be recorded as such, with the PI review of expectedness in relation to the IMP.

For each SAE/SAR/SUSAR the following information will be collected:

- i. full details in medical terms and case description
- ii. event duration (start and end dates, if applicable)
- iii. action taken
- iv. outcome
- v. seriousness criteria
- vi. causality (i.e., relatedness to trial drug / investigation), in the opinion of the investigator
- vii. whether the event would be considered anticipated.

Any change of condition or other follow-up information should be emailed to the Sponsor as soon as it is available or at least within 24 hours of the information becoming available. Events will be followed up until the event has resolved or a final outcome has been reached.

For any other complication, not listed above in section 9.2, occurring within 24 hours of the transplant implantation the information listed above must be collected. However, it will then be the responsibility of the PI to determine whether or not this is likely to be related to the IMP-treatment. If it is deemed likely to be related it will be termed an AR. The PI will also have responsibility for determining the level of seriousness, according to definitions outlined in section 9.1. If an AE/AR is assigned by the PI or delegate (or following central review) as serious it will be termed and SAE/SAR. As there is no reference safety information for either treatment in the trial, all SARs will automatically be treated as SUSARs and will be subject to expedited reporting to the Medicines and Healthcare Products Regulatory Agency (MHRA). The sponsor will inform the MHRA, the REC and Marketing Authorisation Holder of SUSARs within the required expedited reporting timescales.

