Early cessation would be considered if there was a 30% absolute risk reduction in primary graft dysfunction in one treatment arm, as this is the point at which there would be sufficient power to confidently confirm that one arm reduced primary graft dysfunction with a 5% significance level at 80% power. Early cessation will also be considered where the DSMC has concerns that one treatment leads to a significant increase in SARs and/or SAEs.

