9 PHARMACOVIGILANCE

9.1 Definitions

Term	Definition					
Adverse Event (AE)	Any untoward medical occurrence in a participant to whom a medicinal					
	product has been administered, including occurrences which are not					
	necessarily caused by or related to that product.					
Adverse Reaction	An untoward and unintended response in a participant to an investigational					
(AR)	medicinal product which is related to any dose administered to that					
	participant. The physics "manning to an investigational medicinal product" means that					
	The phrase "response to an investigational medicinal product" means that a causal relationship between a trial medication and an AE is at least a					
	reasonable possibility, i.e., the relationship cannot be ruled out.					
	All cases judged by either the reporting medically qualified professional or					
	the Sponsor as having a reasonable suspected causal relationship to the trial					
	medication qualify as adverse reactions. It is important to note that this is					
	entirely separate to the known side effects listed in the SmPC. It is					
	specifically a temporal relationship between taking the drug, the half-life,					
	and the time of the event or any valid alternative aetiology that would					
	explain the event.					
Serious Adverse Event	A serious adverse event is any untoward medical occurrence that:					
(SAE)	• results in death					
	• is life-threatening					
	requires inpatient hospitalisation or prolongation of existing					
	hospitalisation					
	results in persistent or significant disability/incapacity					
	consists of a congenital anomaly or birth defect					
	Other 'important medical events' may also be considered serious if they					
	jeopardise the participant or require an intervention to prevent one of the					
	above consequences.					
	NOTE: The term "life-threatening" in the definition of "serious" refers to					
	an event in which the participant was at risk of death at the time of the					
	event; it does not refer to an event which hypothetically might have caused					
Serious Adverse	death if it were more severe. An adverse event that is both serious and, in the opinion of the reporting					
Reaction (SAR)	Investigator, believed with reasonable probability to be due to one of the					
Macdon (Dill)	trial treatments, based on the information provided.					
Suspected Unexpected	A serious adverse reaction, the nature and severity of which is not					

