9.5 Notification of deaths

All deaths will be immediately reported to the Sponsor. The Sponsor, in combination with the PI will undertake an investigation and make a judgment on the relatedness of the death to the IMP. Where the IMP is felt to have probably contributed to or caused the death this will be termed a SUSAR and the Sponsor will inform the MHRA, the REC and Marketing Authorisation Holder of SUSARs within the required expedited reporting timescales.

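### Sections 9.1, 9.3 and 9.5 set different causality thresholds for a reaction, so a serious event judged possible but not likely is expedited under one test and not under another

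*Protocol*

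**What the plan says.** Four places in the protocol fix how strong a causal link must be before an event counts as a reaction.

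- **Section 9.1, Adverse Reaction row.** The link need only be a "reasonable possibility, i.e., the relationship cannot be ruled out". Either the reporting medically qualified professional or the Sponsor can make that judgement.
- **Section 9.1, Serious Adverse Reaction row.** The event must be "believed with reasonable probability to be due to one of the" trial treatments, in the reporting Investigator's opinion.
- **Section 9.3.** For complications not listed in 9.2 that occur within 24 hours, "it will then be the responsibility of the PI to determine whether or not this is likely to be related to the IMP-treatment". The next sentence reads: "If it is deemed likely to be related it will be termed an AR".
- **Section 9.5, deaths.** The Sponsor, together with the PI, judges relatedness. "Where the IMP is felt to have probably contributed to or caused the death this will be termed a SUSAR".

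Two further passages determine what the label leads to. Section 9.3 states that "all SARs will automatically be treated as SUSARs and will be subject to expedited reporting" to the MHRA. Section 7.10 states: "Early cessation will also be considered where the DSMC has concerns that one treatment leads to a significant increase in SARs and/or SAEs".

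**The concern.** A link that cannot be excluded and a link that is likely are different standards of evidence. Soon after a heart transplant several explanations for an event can coexist, so an assessor may well be able to say neither that the solution caused it nor that it did not. The sections disagree on exactly that answer.

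The disagreement has consequences because this protocol applies no expectedness filter: every SAR is handled as a SUSAR. Once an event is serious, the causality wording alone decides whether it goes to the MHRA, the REC and the Marketing Authorisation Holder on the expedited timescale. It also decides whether the event enters the SAR count, one of the two counts named in the early-cessation sentence of 7.10.

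Who decides differs as well. Section 9.1 lets the Sponsor's view alone make an event a reaction. Section 9.3 gives relatedness to the PI; its mention of central review attaches to seriousness. Section 9.4 has the Chief Investigator or an independent reviewer assign causality only where no local assessment could be obtained. Staff directly involved in the transplant are not blinded (sections 4 and 7.4), and the PI or a delegate generates the allocation (7.3). The person applying the threshold may therefore know the arm, which is a further reason to fix the threshold in one place.

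**Working it through.** No arithmetic applies. The protocol gives no rate for unlisted events within 24 hours and no breakdown by causality grade. The check sets the tests side by side and follows events through them.

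**The tests**

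| Place | Label decided | Causality needed | Whose judgement |
|---|---|---|---|
| 9.1, AR row | AR | Reasonable possibility | Reporting professional or Sponsor |
| 9.1, SAR row | SAR | Reasonable probability | Reporting Investigator |
| 9.3 | AR, then SAR if serious | Likely | PI |
| 9.5 | SUSAR, for a death | Probable contribution or cause | Sponsor with PI |

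**Where they agree.** An event judged likely or probable meets all of these tests. An event for which a causal link is ruled out meets none. They part only for events judged possible but not likely.

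**Event A: serious, not on the 9.2 list, within 24 hours, possible but not likely.**
1. Under the 9.1 AR row it is an AR. Being serious, it would be expected to be a SAR, and 9.3 would then make it a SUSAR with expedited reporting.
2. Under the 9.1 SAR row it may fail, because possibility is not probability. Section 9.1 therefore allows a reaction that is serious without being a serious adverse reaction.
3. Under 9.3 it is not an AR, so it is neither a SAR nor a SUSAR and is not expedited.
4. It is still an SAE. The 9.1 and 9.2 definitions of an SAE contain no causality condition, and 9.3 keeps the SAE label for a serious event that is not a reaction.

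**Event B: the same, but not serious.** It is an AR under 9.1 and not under 9.3. Expedited reporting is unaffected, and 7.10 does not name non-serious ARs.

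**Event C: a death to which the solution possibly, but not probably, contributed.** Under the 9.1 AR row it is a reaction, and it is serious by definition, so it would be expected to reach SUSAR status through 9.3. Under 9.5 it is not a SUSAR. Correcting 9.3 alone would leave this conflict in place.

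**Effect on each count for Event A**

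| Count or action | 9.1 AR test | 9.3 as written |
|---|---|---|
| AR | In | Out |
| SAR | In | Out |
| SUSAR and expedited report | Yes | No |
| SAE | In, as a serious adverse event | In |

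**The case against.** The strongest objection concerns what follows from the conflict. A reader might infer that possible reactions disappear from the counts on which the DSMC acts. The protocol does not support that:

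- The 7.10 sentence names SAEs alongside SARs, and Event A remains an SAE.
- Section 7.10 does not name non-serious ARs, so losing Event B changes no cessation criterion.
- The numeric DSMC triggers in 7.10 (a PGD rate above 50%, 30-day survival below 88.8%) need no causality judgement.
- Section 9.4 has the DSMC review overall safety data. Section 9.3 requires event details, including the investigator's causality opinion, before the reaction label is decided.

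All of this stands. It also means that a distorted safety comparison between the two solutions is not shown.

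A second objection is that few events may be affected. Section 9.2 removes 17 categories of expected complication first, and nothing in the protocol anchors an estimate of what remains. That stands too, and no count is offered here.

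A third is that sites are also referred to separate SAE guidelines and Sponsor procedures, which may already apply a single test. Those documents are not at hand, so it cannot be said that all sites will follow the 9.3 wording or that they will differ from one another. But the protocol itself gives conflicting instructions, and separate guidance does not remove them.

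None of these points answers the effect on SAR classification and expedited reporting.

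**Conclusion.** The inconsistency is real and can be read directly from the text. A serious, unlisted event judged possible but not likely is a reaction due for expedited reporting under the 9.1 AR definition. Under 9.3 it is outside the AR, SAR and SUSAR counts and is not expedited. A parallel conflict exists for deaths under 9.5. The harm is limited to an under-counted SAR tally and missed expedited reports; the events stay in the SAE count and in the data the DSMC sees.

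The size cannot be expressed as a number of events. It does not need to be, since one such event is enough to put two sections of the protocol in conflict over a reporting duty. The conclusion assumes that 9.3 and 9.5 are applied as written and that a serious AR is meant to be a SAR. The primary feasibility outcome is not affected. The correction should be made because it is specific, cheap and concerns safety reporting.

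**What to change.** Use one causality test throughout, the one in the 9.1 Adverse Reaction row: reasonable possibility, meaning that the link cannot be excluded, with either the investigator's or the Sponsor's judgement sufficing.

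1. In 9.3, replace the two sentences on likely relatedness with that test, and say that the Sponsor's judgement alone is enough.
2. In the 9.1 Serious Adverse Reaction row, replace the reasonable-probability wording so that a SAR is simply an AR that is serious.
3. In 9.5, apply the same test to deaths in place of probable contribution.
4. Report AR, SAR and SUSAR counts to the DSMC on this basis, and bring the site SAE guidelines into line if they repeat the 9.3 wording.

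The cost is a few sentences, handled through the amendment process in 13.10. The downside is that a few more events may be classed as reactions and expedited.

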9.4 Responsibilities

All recording and reporting will be completed in accordance with the Sponsor's standard operating procedures.

Principal Investigator (PI):

PIs will additionally have responsibility for checking for AEs and ARs when participants attend for treatment / follow-up and using medical judgement in assigning seriousness, causality and whether the event/reaction was anticipated using the Reference Safety Information approved for the trial.

Chief Investigator (CI) / delegate or independent clinical reviewer:

- 1. Clinical oversight of the safety of patients participating in the trial, including an ongoing review of the risk / benefit.
- 2. Using medical judgement in assigning the SAEs seriousness, causality and whether the event was anticipated (in line with the Reference Safety Information) where it has not been possible to obtain local medical assessment.
- 3. Immediate review of all SUSARs.
- 4. Review of specific SAEs and SARs in accordance with the trial risk assessment and Protocol as detailed in the Trial Monitoring Plan.

- 5. Assigning Medical Dictionary for Regulatory Activities (MedDRA) or Body System coding to all SAEs and SARs.
- 6. Preparing the clinical sections and final sign-off of the Development Safety Update Report (DSUR).

Sponsor: (NB where relevant these can be delegated to CI)

- 1. Central data collection and verification of AEs, ARs, SAEs, SARs and SUSARs according to the trial Protocol onto a database.
- 2. Reporting safety information to the CI, delegate or independent clinical reviewer for the ongoing assessment of the risk / benefit according to the Trial Monitoring Plan.
- 3. Reporting safety information to the independent oversight committees identified for the trial DSMC and / or TSC according to the Trial Monitoring Plan.
- 4. Expedited reporting of SUSARs to the Competent Authority (MHRA in UK) and REC within required timelines.
- 5. Notifying Investigators of SUSARs that occur within the trial.
- 6. Checking for and notifying PIs of updates to the Reference Safety Information for the trial at least annually.
- 7. Preparing standard tables and other relevant information for the DSUR in collaboration with the CI and ensuring timely submission to the MHRA and REC.

Trial Steering Committee (TSC):

In accordance with the Trial Terms of Reference for the TSC, periodically reviewing safety data and liaising with the DSMC regarding safety issues.

Data Safety and Monitoring Committee (DSMC):

In accordance with the Trial Terms of Reference for the DSMC, periodically reviewing overall safety data to determine patterns and trends of events, or to identify safety issues, which would not be apparent on an individual case basis.

9.5 Notification of deaths

All deaths will be immediately reported to the Sponsor. The Sponsor, in combination with the PI will undertake an investigation and make a judgment on the relatedness of the death to the IMP. Where the IMP is felt to have probably contributed to or caused the death this will be termed a SUSAR and the Sponsor will inform the MHRA, the REC and Marketing Authorisation Holder of SUSARs within the required expedited reporting timescales.

9.6 Pregnancy reporting

All pregnancies within the trial (either the trial participant or the participant's partner, with participants consent) should be reported to the Chief Investigator and the Sponsor using the relevant Pregnancy Reporting Form within 24 hours of notification. Pregnancy is not considered an AE regardless of the outcome of the pregnancy, as lack of pregnancy must be confirmed prior to the transplant procedure occurring and any subsequent pregnancy cannot be considered to have been affected by the trial treatment as the treatment will no longer been in the participant's body. Therefore, there will be no additional follow-up of any pregnant participant, or any child born to a pregnant trial participant, or to the partner of a male trial participant.

9.7 Overdose

The trial treatments cannot be overdosed. However, the delegated individuals should provide the volumes of treatment administered in accordance with the trial Protocol.

9.8 Reporting urgent safety measures

If any urgent safety measures are taken the CI/Sponsor shall immediately and in any event no later than 3 days from the date the measures are taken, give written notice to the MHRA and the relevant REC of the measures taken and the circumstances giving rise to those measures.

Please refer to the following website for details on clinical trials safety reporting: http://www.mhra.gov.uk/Howweregulate/Medicines/Licensingofmedicines/Clinicaltrials/Safetyreporting-susandases/http://www.mhra.gov.uk/Howweregulate/Medicines/Licensingofmedicines/Clinicaltrials/Safetyreporting-susandases/http://www.mhra.gov.uk/Howweregulate/Medicines/Licensingofmedicines/Clinicaltrials/Safetyreporting-susandases/http://www.mhra.gov.uk/Howweregulate/Medicines/Licensingofmedicines/Clinicaltrials/Safetyreporting-susandases/http://www.mhra.gov.uk/Howweregulate/Medicines/Licensingofmedicines/Licens

9.9 The type and duration of the follow-up of participants after adverse reactions

Any SAE or SAR that occurs within 24 hours of the transplant procedure will be recorded, as outlined above. Where this is thought to be due to the trial treatment, the participant will be looked after by their transplant team. The PI or delegated individual will follow-up the participant on discharge from ICU and on discharge from hospital, with an in-person discussion of the SAE/SAR. Their further clinical follow-up will be determined by their transplant team.

9.10 Development safety update reports

The CI will provide (in addition to the expedited reporting above) DSURs once a year throughout the clinical trial, or as necessary, to the Competent Authority (MHRA in the UK), where relevant the Research Ethics Committee and the sponsor.

The report will be submitted within 60 days of the Developmental International Birth Date (DIBD) of the trial each year until the trial is declared ended.

10 STATISTICS AND DATA ANALYSIS

10.1 Sample size calculation

This is a feasibility study, so formal sample size calculation is not required. However, 50 hearts will give a 95% confidence interval of 53%-79% assuming a primary outcome rate of 66%.

10.2 Planned recruitment rate

A proportion of two-thirds for the primary outcome will be considered successful, as it would correspond to a yearly average of approximatively 80 patients being recruited in the main study, assuming a yearly number of available hearts of 120 (corresponding to the yearly observed number of adult DBD heart transplants in the UK during the last two years).

A power calculation for a superiority trial based on the development of primary graft dysfunction as the primary outcome showed that a sample size of 400 patients would allow detection of a 14% absolute risk reduction in PGD between the two solutions of interest (from 36% to 22%) corresponding to an odds ratio of 0.5 (or 17 cases of PGD prevented per year) with a probability (power) of 0.85 with a type I error of 0.05 when considering a two-sided test of difference in proportions. As approximately 120 adult DBD heart transplants are performed in the UK each year, we estimate that the larger trial will take 5 years to complete (i.e., $80 \times 5 = 400$).

For this feasibility trial to meet its recruitment target, we anticipate a recruitment rate of 80 patients per year, over a period of 6-12 months. 1 patient per site per month would result in a 9-month recruitment period.

10.3 Statistical analysis plan

10.3.1 Summary of baseline data and flow of patients

The following baseline data will be collected for all eligible donors:

- i. Consent to participate in research, a categorical variable with categories yes/no, reported as proportions
- ii. age, a continuous variable which will be reported as mean age at time of donation
- iii. sex, a categorical variable, which will be reported as proportions of male, female or other
- iv. ethnicity, a categorical variable, which will be reported as proportions of each category, with the categories being:
 - a) Asian or Asian British
 - Indian
 - Pakistani
 - Bangladeshi
 - Chinese
 - Any other Asian background
 - b) Black, Black British, Caribbean or African
 - Caribbean
 - African
 - Any other Black, Black British, or Caribbean background
 - c) Mixed or multiple ethnic groups
 - White and Black Caribbean
 - White and Black African
 - White and Asian

- Any other Mixed or multiple ethnic background
- d) White
 - English, Welsh, Scottish, Northern Irish or British
 - Irish
 - Gypsy or Irish Traveller
 - Roma
 - Any other White background
- e) Other ethnic group
 - Arab
 - Any other ethnic group

The following baseline data will be recorded for eligible donors whose family consent but who are not randomised:

i. the reason not randomised. This will take the form of free-text qualitative data, which will be analysed and grouped into categories for reporting by the trial steering committee.

The following baseline data will be collected for all other eligible donors:

- i. ABO blood group, a categorical variable with groups A, B, AB and O, reported as proportions
- ii. Height, a continuous variable, measured in cm and reported as means
- iii. Weight, a continuous variable, measured in kg and reported as means
- iv. BMI (kg/m²), a continuous, calculated variable determined as weight in kg divided by height in metres, squared and reported as means
- v. Pathology leading to brainstem death, a categorical variable with groups anoxia, stroke, trauma, malignancy and other and reported as proportions
- vi. History of Hypertension, a categorical variable with categories yes/no, reported as proportions
- vii. History of Pulmonary disease, a categorical variable with categories yes/no, reported as proportions
- viii. History of Cardiac disease, a categorical variable with categories yes/no, reported as proportions
 - ix. History of Liver disease, a categorical variable with categories yes/no, reported as proportions
 - x. History Diabetes mellitus, a categorical variable with categories yes/no, reported as proportions
 - xi. Insulin use, a categorical variable with categories yes/no, reported as proportions
- xii. Renal function (serum creatinine), a continuous variable with serum creatinine at time of donation in milligrams per decilitre (mg/dL) reported as mean
- xiii. Liver function (bilirubin), a continuous variable measured on serum sample at the time of donation in milligrams per decilitre (mg/dL) and reported as mean
- xiv. History of Infection from any source during admission, treated with antibiotics, a categorical variable with categories yes/no, reported as proportions
- xv. History of Malignancy, a categorical variable with categories yes/no, reported as proportions
- xvi. Left Ventricular Ejection Fraction, a continuous variable measured on the echocardiogram closest to the time of donation and given as a percentage, reported as means
- xvii. Ischaemic time, a continuous variable measured in minutes, reported as medians
- xviii. Current or past smoker, a categorical variable with categories yes/no, reported as proportions
- xix. History of Drug abuse, a categorical variable with categories yes/no, reported as proportions

vx. Vasoactive Inotrope score (VIS), a continuous variable calculated as VIS = dopamine (×1) + dobutamine (×1) + amrinone (×1) + milrinone (×15) + adrenaline (×100) + noradrenaline (×100), with each drug dosed in $\mu g/kg/min$. using the maximum dosing rates of vasoactive and inotropic medications ($\mu g/kg^{-1} min^{-1}$) or IU $kg^{-1} min^{-1}$) in the 24 h prior to organ donation, reported as medians

The following baseline data will be collected for all eligible recipients:

- i. Approach to consent, a categorical variable with categories yes/no, reported a proportions
- ii. age, a continuous variable, which will be reported as mean age at time of donation
- iii. sex, a categorical variable, which will be reported as proportions of male, female or other
- iv. ethnicity, a categorical variable, which will be reported as proportions of each category, with the categories being:
 - a) Asian or Asian British
 - Indian
 - Pakistani
 - Bangladeshi
 - Chinese
 - Any other Asian background
 - b) Black, Black British, Caribbean or African
 - Caribbean
 - African
 - Any other Black, Black British, or Caribbean background
 - c) Mixed or multiple ethnic groups
 - White and Black Caribbean
 - White and Black African
 - White and Asian
 - Any other Mixed or multiple ethnic background
 - d) White
 - English, Welsh, Scottish, Northern Irish or British
 - Irish
 - Gypsy or Irish Traveller
 - Roma
 - Any other White background
 - e) Other ethnic group
 - Arab
 - Any other ethnic group

The following baseline data will be recorded for eligible recipients who are approached but do not consent:

i. the reason for declining to take part (where given). This will take the form of free-text qualitative data, which will be analysed and grouped into categories for reporting by the trial steering committee.

The following baseline data will be collected for all eligible recipients who consent and receive a transplant:

- i. ABO blood group, a categorical variable with groups A, B, AB and O, reported as proportions.
- ii. Height, a continuous variable, measured in cm and reported as means.
- iii. Weight, a continuous variable, measured in kg and reported as means.

- iv. BMI (kg/m²), a continuous, calculated variable determined as weight in kg divided by height in metres, squared and reported as means.
- v. Pathology leading to need for transplant, a categorical variable with groups dilated cardiomyopathy, ischaemic cardiomyopathy, hypertrophic cardiomyopathy, restrictive cardiomyopathy, congenital heart disease, valvular heart disease and other, reported as proportions.
- vi. Transplant number, an ordinal variable with values, 1, 2, 3 or more, reported as proportions.
- vii. History of Hypertension, a categorical variable with categories yes/no, reported as proportions.
- viii. History of Diabetes mellitus, a categorical variable with categories yes/no, reported as proportions.
- ix. Renal function (eGFR and serum creatinine), continuous variables with serum creatinine at time of donation in milligrams per decilitre (mg/dL) and eGFR calculated using the Cockroft-Gault equation, reported as means.
- x. Liver function (bilirubin), a continuous variable measured on serum sample at the time of donation in milligrams per decilitre (mg/dL) and reported as means.
- xi. Infection from any source, treated with antibiotics, a categorical variable with categories yes/no, reported as proportions.
- xii. Left Ventricular Ejection Fraction, a continuous variable measured on the echocardiogram closest to the time of but prior to the transplant and given as a percentage, reported as means.
- xiii. Smoking, a categorical variable with categories current, previous and never, reported as proportions.
- xiv. Drug abuse, a categorical variable with categories current, previous and never, reported as proportions.
- vv. Vasoactive Inotrope score (VIS), a continuous variable calculated as VIS = dopamine (×1) + dobutamine (×1) + amrinone (×1) + milrinone (×15) + adrenaline (×100) + noradrenaline (×100), with each drug dosed in $\mu g/kg/min$. using the maximum dosing rates of vasoactive and inotropic medications ($\mu g kg^{-1} min^{-1}$) or IU $kg^{-1}min^{-1}$) in the 24 h prior to the transplant implantation, reported as medians.
- xvi. Mechanical Circulatory Support, a categorical variable with categories None, VA-ECMO, VV-ECMO, IABP, LVAD, RVAD, BiVAD, TAH, Impella and Other, determined by their use at the time of transplant (prior to implantation) and reported as proportions.
- xvii. Previous cardiac surgery, a categorical variable with categories yes/no, reported as proportions.
- xviii. Pre-operative mean pulmonary artery pressure (mmHg), pulmonary capillary wedge pressure (mmHg), cardiac output (L/min) and cardiac index (L/min/m2), continuous variables taken from the right heart catheter prior to transplant implantation, reported as medians.

A consort flow diagram will be produced and appended to this Protocol. This will evaluate all eligible transplant procedures as part of the primary outcome of this feasibility study, but will also record all patients approached to consent, some of whom may not be included in the primary outcome, for example recipients who have been approached to consent prior to their transplant but do not receive a transplant within the study period.

